After a subject consents to be in the study, baseline demographic data will be collected for each subject including age, sex, height, weight, and Fitzpatrick skin type (determined by a member of the study team); information regarding current medical conditions will also be collected. Specifically, the subject's approximate duration of each condition, what treatments the subject has received, and approximate severity of the conditions will be collected, as well as a current medication list. All of this information will be collected directly from the subject and the subject's medical record will not be reviewed/abstracted for research data. After completing the questionnaire a member of the research team will determine if the subject is eligible to continue participating in the study. Subjects will be screened out after this process if their answers to screening questions meet the exclusionary criteria. Consent and screening procedures will require approximately 1 hour.

On the first day of study procedures (Day 0), which may occur on the same day as the consenting process, subjects will first be asked to sit quietly in the CRU for 30 minutes before any study procedures are started, in order for their skin to acclimate to the room temperature and humidity. Nine sites will be identified on the upper arm and marked with a pen. At all marked sites baseline measurements of hydration, colorimetry, trans-epidermal water loss, and impedance will be measured at each site, using noninvasive flat probes (described below). The probes are attached to a computer that calculates measurement units. Three sites will receive the micropatch treatment (described below), and after treatment the trans-epidermal water loss and impedance measurements are repeated and the sites will be covered by blank occlusive material secured to the skin with medical tape. Three of the sites will receive no micropatch treatment but will be covered with occlusive material. Three of the sites will serve as controls and will receive no treatment and they will remain uncovered. Study procedures on this first day (Day 0) will require approximately 2 - 3 hours. Hair may be clipped (but not shaved) at the identified sites prior to start of the study procedures, if necessary.

The following procedure will be used to apply the micropatch for each subject:

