The micropatch will be placed perpendicularly to the skin surface and the microneedles will be inserted by the application of gentle force to the back of the array (the study team member will apply this gentle pressure with their thumb or use of a hand-held applicator). The pressure will be applied for approximately 10 seconds and then the patch will be removed. The patch will be rotated 45 degrees and the same process will be repeated, in order to create a total of 100 non-overlapping pores. The micropatch treatment will only occur on the first study day.

The following procedure will be used to make the baseline and all following measurements of the 9 identified sites:

Several quick measurements will be made at each site, using noninvasive probes.

- Transepidermal water loss (TEWL) will be measured at each site by placing a small probe on the surface of the skin for approximately 1 - 3 minutes at each site. This measurement will not be repeated after Day 0 procedures.
- The hydration level of the skin will be measured at each site by placing a corneometer probe lightly on the skin; each measurement takes less than 1 minute at each site.
- The redness and color of the skin will be measured at each site by placing a colorimetry probe on skin for less than 1 minute at each site.
- Impedance will be measured using an impedance meter with a series of electrodes. This process takes approximately 2 minutes at each site.

Subjects will be asked to return to the CRU at 24 hour intervals for 4 days (24, 48, 72, and 96 hours) after microneedle insertion. At each of these return visits the baseline measurements will be repeated (excluding TEWL measurements). Occlusive coverings will be removed before measurements are taken, and fresh material will be applied afterwards. Each visit will last approximately 1 1/2 - 2 hours.

Within 2 to 3 days following completion of the study, one of the study team members will follow up with the subject via phone or email to determine if the subject is having any redness or skin irritation at the site of any of the treatments. There is no long-term follow up necessary. The overall time commitment for the subjects is approximately 11 - 14 hours with 5 study days (6 if consent and Day 0 procedures do not occur on same day) over 1 week.

VII.E.7 *Will you attempt to recontact subjects who are lost to follow-up?*

No - those lost to followup will not be recontacted

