Descriptive statistics will be used for subject demographics. Each subject will serve as their own control, and paired t-tests will determine differences in TEWL (water loss measurements) from baseline to post-microneedle insertion (this is used to determine if the microneedles adequately breached the skin barrier). For the colorimetry and hydration measurements, each daily measurement will be compared to its baseline at that site using paired t-tests. The percent change in TEWL measurements from baseline to post-microneedle application will be calculated and compared between groups.

The impedance data for this study will be analyzed using similar methods as our previous study. The Z-pores impedance value will be calculated, and Student's t-tests will be used to ensure that micropores were adequately created (demonstrated by a significant decrease in impedance from baseline). Next, Z-pores will be calculated from impedance measurements taken over several hours to days following microneedle treatment (depending on the subject group), and then converted to admittance (admittance is the inverse of impedance). The admittance can demonstrate how "open" the micropores are in a very intuitive manner. If a micropore has a maximum admittance, then the micropore is 100% open. Using this information, we will plot admittance vs. time and calculate a rate constant of micropore admittance (k). The rate constant is then used to calculate the half-life of micropore closure, which thus describes a rate of closure in units of time.

XI.2 *Provide the rationale or power analysis to support the number of subjects proposed to complete this study.*

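### The colour and hydration t-tests are written at site level with three replicate sites per condition per subject, and XI.1 has no step that averages them or accounts for subject

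*Combined protocol and SAP*

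**What the plan says.** **Design (VII.E.6).** "Nine sites will be identified on the upper arm and marked with a pen". Three sites get the micropatch and are then occluded. Of the other six, "Three of the sites will receive no micropatch treatment but will be covered with occlusive material", and "Three of the sites will serve as controls and will receive no treatment and they will remain uncovered". Hydration and colour are both read at every site, at baseline and again at 24, 48, 72 and 96 hours. The section does not tie particular positions on the arm to particular conditions.

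**Analysis (XI.1).** For colour and hydration, "each daily measurement will be compared to its baseline at that site using paired t-tests". For TEWL before and after insertion, "Each subject will serve as their own control, and paired t-tests will determine differences in TEWL". Impedance before and after insertion is also compared by t-test, as a check that pores were created. For none of these measures does XI.1 say how the three sites in a condition are combined. It names no subject-level summary, mixed model or clustered variance.

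**No other source.** VII.B.11 states that there is no separate written protocol, so within these documents XI.1 is the whole analysis plan.

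**The concern.** A paired t-test needs independent pairs. Here the independent units are the subjects, while the rule for colour and hydration is written for the site. Pairing each reading with the same site's baseline removes stable differences between sites and between people. It does not remove correlation among the three *changes* on one person. Those sites share an arm, a visit, a covering regimen and one person's skin response, and the study's own hypothesis (I.5) is that skin recovery differs systematically between groups of people.

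If the three sites enter as three pairs, the number of pairs is three times the number of subjects. The standard error is then too small, and changes from baseline are declared too often. XI.2 says that the pilot is to supply data for a later power analysis, so a variance or sample size counted in sites could carry the error forward. Leaving the rule open also lets the choice be made after the data are seen.

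**Working it through.** **The plan's own figure.** XI.2 gives six categories of 10 and one of 20 in each of two BMI groups: 2 × (6 × 10 + 20) = 160, which matches the target enrolment in VI.13. It is a feasibility number. The documents give no alpha, power or standard deviation for these tests, so there is no precision figure to reproduce.

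**Inputs.**
- Replicate sites per subject and condition: m = 3 (VII.E.6).
- Subjects per test: 10 assumed, the smallest planned category in XI.2; 20 as a check, the planned Asian category.
- Test: two-sided 5%, assumed.
- ICC of the changes from baseline among a subject's sites: not in the documents; 0 to 0.7 assumed.

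**Formulas.** The design effect is 1 + (m − 1) × ICC = 1 + 2 × ICC. The naive standard error divided by the true one is 1/√(design effect). The effective number of pairs is 30/(design effect), since 10 subjects × 3 sites = 30.

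For ICC 0.5: the design effect is 1 + 2 × 0.5 = 2.0, the ratio is 1/√2 = 0.71, and the effective number is 30/2 = 15.

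**Results for 10 subjects** (simulated type I error, 40,000 runs per row):

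| ICC | Design effect | Naive SE / true SE | Effective pairs | 30 site pairs | 10 subject means |
|---|---|---|---|---|---|
| 0 | 1.0 | 1.00 | 30.0 | 5.0% | 5.0% |
| 0.1 | 1.2 | 0.91 | 25.0 | 7.6% | 5.3% |
| 0.3 | 1.6 | 0.79 | 18.8 | 12.2% | 5.0% |
| 0.5 | 2.0 | 0.71 | 15.0 | 17.0% | 5.0% |
| 0.7 | 2.4 | 0.65 | 12.5 | 21.7% | 4.8% |

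With 20 subjects the site-pair column is 4.9%, 7.5%, 11.9%, 16.9% and 21.2%. A larger category does not cure the problem.

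**Other readings.** Testing one site position at a time across subjects also holds about 5% per test. It gives 9 × 4 × 2 = 72 tests instead of 3 × 4 × 2 = 24 (positions or conditions × days × measures, one value per measure). The 24 tests remain after averaging, so multiplicity is a separate matter.

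**A mixed model is not automatically a cure.** Random intercepts for subject and for site cancel from a change-from-baseline contrast, so the correlation among changes stays unmodelled. In simulation, that model gave a type I error of about 13%, 17% and 22% at ICC 0.3, 0.5 and 0.7, much the same as pooling the sites.

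**The case against.** The strongest reply is that XI.1 never says sites are counted as independent pairs. The phrase about the baseline at that site fixes which baseline each reading is matched to; it does not fix how many pairs enter the test. The words also allow matching by site and then averaging within subject, or one test per site position. Neither of those understates the standard error. This stands: a reader might infer that the plan commits to 30 pairs from 10 subjects and that its error bars will be too small, and the documents do not support that as fact. Pooling is the plainest literal reading, however, because nothing mentions averaging and site positions are never tied to conditions.

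Three further limits also stand.
- XI.1 does not say that the tests are run within each race-by-BMI category, so the 10 subjects are an assumption. Inflation in every such category cannot be claimed.
- The TEWL sentence has no site-level wording. It speaks of each subject as their own control, and the test only checks that the barrier was breached. All that can be said there is that replicate handling is unstated; the same goes for impedance.
- Pairing on baseline may leave little correlation. At ICC 0 there is no inflation, and at 0.1 it is mild.

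On weight, the research question is answered by the impedance-based closure half-life. Colour and hydration are supportive measures in a pilot, and no decision rule hangs on them. This limits the importance of the point but does not remove it.

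**Conclusion.** The point holds in this form: XI.1 sets the colour and hydration tests at the level of the site, each subject supplies three replicate sites per condition, and nothing averages them or accounts for subject. If sites are the pairs, a nominal 5% test has a true level between about 5% (ICC 0) and about 22% (ICC 0.7). This rests on an assumed ICC, an assumed 10 subjects and an assumed two-sided 5% level. Analysis of subject means keeps about 5% throughout. The documents do not show that the inflated analysis will be run, only that their wording leads there most directly and does not rule it out. The enrolment target is unaffected. The change is worth making because it is nearly free, but it does not by itself call the half-life result into question.

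**What to change.** In XI.1, state that the subject is the unit of analysis. The three replicate sites should be averaged within subject, condition and day before any paired t-test, giving one value per subject in each test. Use the same subject-level value for the TEWL and impedance comparisons.

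If a mixed model is preferred, it needs a subject-by-condition-by-day random effect and a day-by-condition term. Alternatively, model the change scores with a random subject effect, for one condition and day at a time. Subject and site intercepts alone are not enough. Averaging is the simpler option.

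The cost is a sentence or two, with no new data and no more subjects. The downside is that some p-values become less favourable.

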The research question we are seeking to answer is whether there are differences in the time it takes for the skin to completely repair after micropatch application in subjects of different race and ethnicities. We hypothesize that the skin of non-Caucasian individuals will restore barrier function more quickly than in Caucasians.

- I.6** *Background and significance and/or Preliminary studies related to this project.
(do not indicate "see protocol")*
Transdermal drug delivery (by way of patches that adhere to the skin and deliver drug in a time-dependent fashion) allows for systemic drug delivery through the skin, while avoiding many of the side effects and challenges associated with oral or intravenous drug delivery. One significant challenge limiting the number of drug compounds that can be transdermally delivered is the hydrophobic nature of the skin, which provides a highly efficient barrier against the absorption of drug molecules. Microneedles are a minimally invasive means of assisting the transport of drug molecules across the skin by creating micron-sized channels (also called micropores) in the skin, thereby increasing its permeability. Many studies have demonstrated that microneedle treatment is relatively painless and well-tolerated by most patients.

Following microneedle treatment, the skin must heal the micropores in order to restore barrier function. In young healthy individuals this process takes approximately 48 – 72 hours when the skin is covered by an occlusive patch. The timeframe for micropore closure is longer in elderly individuals (>65 years of age), taking several days longer to restore the skin barrier. As evidenced by the differences in micropore closure rate observed with advancing age, biological variation can have a significant effect on the skin's healing properties. There are almost no data available regarding how race and ethnicity affect skin response to microneedle insertion. It is crucial to better understand how the rates of micropore closure vary in different racial/ethnic populations because the potential for variability in drug delivery is high if the recovery timeframes are poorly understood.

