No direct patient identifiers will be recorded on data collection material. Instead, subjects will be assigned a subject number on study materials. Only the data necessary to answer the research question will be collected, and all consent processes and study procedures will take place in a private location in the Clinical Research Unit.

X.2

Are you collecting the Social Security Number of any subjects for any purpose?

Yes

X.3

Provide the intended usage of SSN:

- To provide compensation to subjects

X.4

How will information/data be collected and stored for this study (check all that apply):

- Paper/hard copy records (hard copy surveys, questionnaires, case report forms, pictures, etc.) - Hard copies will only be transported by members of the research team. Hard copies will be stored in the office of the Clinical Coordinator in C44-P of the ICTS center of UIHC or in the office of the Clinical Coordinator in 558 CPB in a locked filing cabinet only accessible to members of the study team. Upon closure of the study documents will be stored in the office of the Clinical coordinator in 558 CPB or in B105 and B109 ML.
- Electronic records (computer files, electronic databases, etc.) - Electronic results and data (after direct patient identifiers have been removed) will be kept on a password protected shared drive (College of Pharmacy, University of Iowa) that only members of the research team will be able to access.
 - Name - [name]
 - Title - IT Director

- o University Job Classification - Faculty/Staff

X.5 *Do the confidentiality protections indicated above allow only members of the research team to access the data/specimens?*
 Yes

X.7 *Does your study meet the NIH criteria for a [Certificate of Confidentiality](#), or will you be applying for Certificate of Confidentiality?*
 No

XI. Data Analysis

XI.1 *Describe the analysis methods you will use, including, if applicable, the variables you will analyze*

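### The closure rate constant has no fixed fitting rule, no described masking to race or BMI group, and a reading window said to vary by group

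*Combined protocol and SAP*

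**What the plan says.** - **Derivation (XI.1).** Impedance is converted to admittance, and then "we will plot admittance vs. time and calculate a rate constant of micropore admittance (k". Next, "The rate constant is then used to calculate the half-life of micropore closure". No model, estimation method, baseline or residual handling, combination of the three treated sites, or exclusion rule is given.
- **Source of the method (XI.1).** "The impedance data for this study will be analyzed using similar methods as our previous study". That study's methods are not written out, and VII.B.11 says there is no separate written protocol.
- **Readings used (XI.1).** The pore impedance comes from measurements "taken over several hours to days following microneedle treatment (depending on the subject group". XI.1 does not define the group. I.4 divides subjects by self-identified race and BMI; XI.2 names two BMI groups with race cells inside each.
- **Schedule (VII.E.6).** "Subjects will be asked to return to the CRU at 24 hour intervals for 4 days (24, 48, 72, and 96 hours". With the post-treatment reading on Day 0, every subject has the same five post-treatment time points.
- **Hypothesis (I.5).** "We hypothesize that the skin of non-Caucasian individuals will restore barrier function more quickly than in Caucasians".
- **Coding (X.1, X.4).** "Instead, subjects will be assigned a subject number on study materials", and direct identifiers are removed from electronic data. Both appear as confidentiality measures.
- **Group information held by the team.** Self-identified race is asked at pre-screening (VII.D.20) and recorded after consent (VII.D.26). A team member assigns Fitzpatrick type (VII.E.6).
- **Design.** Subjects are not randomised (VII.E.1), and no masking is described for any step.

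**The concern.** The impedance readings come from an instrument, but k does not. It depends on which time points enter the fit, whether a residual admittance after closure is modelled, how three sites become one value, and what counts as a bad reading. XI.1 settles none of these. Its one remark on which readings are used makes them depend on group, so as written, group can enter the derivation of the outcome on which the groups differ or agree.

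This matters because half-life is the only quantity in XI.1 that expresses closure rate. Water loss is not repeated after Day 0 (VII.E.6), so it cannot serve as a cross-check. The hypothesis has a stated direction, the comparison is non-randomised, and most race cells hold 10 subjects per BMI group (XI.2). XI.2 also says the results will feed a later power analysis, so a distorted group difference would carry forward into it.

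**Working it through.** **1. The plan's own figure.** XI.2 gives cells per BMI group of 10 + 10 + 10 + 20 + 10 + 10 + 10 = 80, and 2 × 80 = 160, which matches the target in VI.13. No alpha, effect size, SD or power is stated, so no other figure bears on this point.

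**2. The two sections side by side.** XI.1 describes measurements from several hours to days, depending on group. VII.E.6 schedules a post-treatment reading on Day 0 and then 24, 48, 72 and 96 h for everyone. No schedule varies by group, and no visit falls between Day 0 and 24 h. Either the readings that enter the fit vary by group although the visits do not, or the XI.1 phrase does not describe this study. The documents do not say which.

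**3. How far the window alone can move a half-life.** Only the time points come from the plan (VII.E.6). The half-life, residual and model are assumptions. For orientation, I.6 puts closure in young healthy people at about 48 to 72 h under occlusion.

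For one noiseless subject with true half-life h and residual fraction f, relative admittance is A(t) = (1 − f)·exp(−ln 2 · t/h) + f. A straight line is fitted to ln A by least squares; half-life = ln 2 / |slope|.

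Example, h = 14 h and f = 0.05: ln A at 0, 24, 48, 72, 96 h is 0, −1.0802, −1.9788, −2.5654, −2.8440.
- 0-48 h: slope = −1.9788/48 = −0.04123 per h; half-life = 0.6931/0.04123 = 16.8 h.
- 0-96 h: slope = [(−24)(−1.0802) + 24(−2.5654) + 48(−2.8440)]/5760 = −172.16/5760 = −0.02989 per h; half-life = 23.2 h.
- Ratio 23.19/16.81 = 1.38, a 38% shift.

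| True half-life | Residual | 0-48 h fit | 0-96 h fit | Shift |
|---|---|---|---|---|
| 14, 18 or 24 h | 0 | true value | true value | 0% |
| 14 h | 2% | 15.1 h | 18.4 h | 22% |
| 14 h | 5% | 16.8 h | 23.2 h | 38% |
| 18 h | 2% | 19.1 h | 21.2 h | 11% |
| 18 h | 5% | 20.7 h | 25.3 h | 22% |
| 24 h | 2% | 25.1 h | 26.4 h | 5% |
| 24 h | 5% | 26.7 h | 29.9 h | 12% |

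The shift vanishes without a residual and grows as closure gets faster relative to the 96 h of follow-up.

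**4. What masking and fixed rules would each prevent.** A null simulation with no true race difference compared 20 Caucasian subjects (2 × 10) with 140 others (160 − 20), using a two-sided t-test on log half-life at 0.05 and 500 replicates per scenario. Assumptions: half-life 12, 18 or 24 h; between-subject CV 30%; log-scale noise 0.15 or 0.30; residual 0 or 3%; five plausible log-linear fits.
- One fixed fit for everyone: 3.6% to 7.2% false positives.
- Discretionary choice of fit in 10% or 25% of subjects, unrelated to race: 3.2% to 7.4%.
- The same discretion always exercised toward the hypothesis: 5.0% to 27.6% (10% of subjects) and 6.6% to 92.6% (25%). This is a deliberate worst case.
- One fit chosen for the whole study after seeing results: 3.2% to 9.4% in the hypothesised direction, against a nominal 2.5%.

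The third line shows the route that masking closes. The fourth shows a route that masking alone leaves open and that rules fixed beforehand close.

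**The case against.** The strongest reply is that the documents show no biased step. XI.1 does not say who derives k, what that person sees, or that points are picked by hand; the cited earlier study may fix the model and the points. A reader might infer that k is fitted with race known. The documents do not support that: they are silent in both directions. What stands is narrower: no masking is described, no rule is written here, and the only text on which readings are used ties them to group.

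A reader might also infer that the existing subject numbers already make masked derivation possible. They do not by themselves. X.1 and X.4 remove direct identifiers, not race, and colorimetry is measured at the same sites. A separate extract is needed.

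The window calculation contains no groups. If either window is applied to everyone, groups with the same true closure get the same half-life. That objection is correct, and it limits the calculation to showing sensitivity.

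Finally, XI.2 calls this a pilot, and XI.1 names no between-group test for k or half-life; only percent change in water loss is said to be compared between groups. This lowers the weight of formal error rates. It does not remove the concern, because the question in I.5 is about closure time by race.

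**Conclusion.** The point holds as a cheap improvement. As written, the plan leaves a route by which group can enter the derivation of the only closure-rate outcome: no fit or exclusion rule, a window said to depend on group against a common visit schedule, no described masking, and a directional hypothesis.

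The size of any resulting bias is unknown. The 0% to 38% range rests on assumed half-lives of 14 to 24 h, residuals of 0 to 5% and a straight-line fit of log admittance. It must not be read as a group difference. Nor should the upper simulated error rates be read as a forecast, since they require every discretionary choice to go the same way.

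**What to change.** In XI.1, state that:
- k and half-life are derived for every subject with one named model (including how residual admittance is handled), one common time window, one rule for combining the three treated sites and one exclusion rule, all fixed before the data are examined;
- the derivation uses an extract holding only subject number, site condition, time and impedance, with no race, BMI, Fitzpatrick type or colorimetry, and preferably by someone who did not measure the subjects;
- every excluded reading is logged with its reason;
- the derived dataset is frozen before race and BMI group are merged.

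Also reconcile the group-dependent wording in XI.1 with the common schedule in VII.E.6, and define the group if the wording is kept.

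The cost is a short addition to XI.1, preparation of a separate extract, and a short delay before group results can be seen. If a deriver who took no measurements is wanted, that person has to be named. No new data, visits or subjects are needed.
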